#### CONFIDENTIAL

This material is the property of the NYU School of Medicine and Langone Medical Center.  
Do not disclose or use except as authorized in writing by the study sponsor (if applicable).

on which a new 2D CT image is generated. Each observer then manually selected the anterior and posterior aspect of the glenoid on this 3D-corrected image, and version was determined according to the Friedman et al. (17) The new CT image along the transverse scapular plane is generated according to the following procedure. The true coronal scapular plane passed through the 3 points. The scapular axis was defined as the line passing through the center of the glenoid and the medial pole of the scapula. The transverse scapular plane was perpendicular to the coronal scapular plane and passed through the scapular axis. A new CT image along the transverse scapular plane is generated from the original CT data set using the Vitrea workstation.

MRI is performed using 3T scanners with a dedicated 16-channel shoulder array coils. The MRI sequences include 3-mm slice thickness and 0.5-mm gap width with a field of view of 14 or 15 cm. There were 6 diagnostic sequences with axial, coronal, and sagittal proton density weighting as well as coronal T2 with frequency selective fat suppression and sagittal T1 images. The protocol also included an axial 3D dual echo-time T1-weighted FLASH sequence with Dixon-based water-fat separation with the following parameters: TR 10, TE 2.45/3.7, field of view of 200 mm, acquired voxel size 1.0×1.0×1.4 mm, reconstructed voxel size 1.0×1.0×1.0 mm, flip angle 9 deg, matrix 192×192, bandwidth of 400 Hz/pixel, number of partitions=120 and a slice thickness of 1mm.

MRI 3D Post-processing: The water-only source images from the Dixon sequence were post-processed using standard subtraction software on a syngo MMWP workstation (VB 3oE, Siemens). The lowest mean signal intensity (water min) from multiple ROIs placed on the soft tissues surrounding the osseous structures was used as a constant to calculate a subtraction image where the pixel values are subtracted from this constant (water\_min – SI (i) with negative values being set to zero). This resulted in images with increased signal in the osseous structures, surrounded by signal poor/void soft tissue structures. These subtracted Dixon images then underwent manual segmentation, generating 3D reconstructions of each shoulder (Tera Recon software (4.4.5.36.2068)).

The 3D MRI glenoid version is measured by the two observers with the same method used for CT 3D glenoid version measurement following generating a new 2D axial MR images from the 3D MRI model using the three-point method as described above.

### **Data Analysis**

Using SAS software, version 9.4 (SAS Institute Inc., Cary, NC, USA) Paired sample t-test to compare measurements by model and ANOVA to assess differences among modalities.

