## Study Summary

Title	Preoperative Magnetic Resonance as an Alternative to Computed Tomography Three-Dimensional Imaging for Characterizing Bone Loss in Shoulder Arthroplasty Candidates with Glenohumeral Osteoarthritis: A prospective, blinded, and controlled clinical trial.
Short Title	3D MR versus 3D CT in Glenohumeral Osteoarthritis
Protocol Number	S17-00500
Methodology	A prospective, unrandomized, single-blinded, self-controlled, and single-armed diagnostic radiological evaluation study.
Study Duration	12-Months
Study Center(s)	Single-Center
Purpose	To examine the non-inferiority of three-dimensional (3D) magnetic resonance (MR) versus the gold-standard, 3D computed tomography (CT) imaging, in the analysis of bone loss in shoulder arthroplasty (SA) candidates with glenohumeral osteoarthritis (OA). This study does not assess the safety and efficacy of MR imaging for musculoskeletal disorders.
Number of Subjects	50 subjects
Diagnosis and Main Inclusion Criteria	Patients with glenohumeral OA who are candidates for SA based on clinical examination with radiographic evidence of significant glenoid wear ; males and females age 18 and above.
Study Intervention and Planned Use	3D MR imaging of the shoulder for evaluation of glenoid bone loss.
Reference Intervention	3D CT imaging of the shoulder for evaluation of glenoid bone loss.
Statistical Methodology	Paired sample t-test to compare measurements by model and ANOVA to assess differences among modalities.

CONFIDENTIAL

This material is the property of the NYU School of Medicine and Langone Medical Center.  
Do not disclose or use except as authorized in writing by the study sponsor (if applicable).

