## I. PURPOSE OF THE STUDY AND BACKGROUND

### **Purpose**

The purpose of this study is to examine the noninferiority of 3-dimensional (3D) magnetic resonance (MR) as an alternative to 3D computed tomography (CT) imaging to characterize glenoid bone loss in shoulder arthroplasty (SA) candidates with glenohumeral osteoarthritis and radiographic evidence of severe glenoid erosion. MR has been routinely used in musculoskeletal imaging with and without contrast. This study employs no non-FDA approved investigational MRI hardware or software.

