### **Background & Study Rationale**

There has been over a five-fold growth in incidence of shoulder arthroplasty (SA) for glenohumeral osteoarthritis (OA) since 2000 (1) (2) (3) (4). Asymmetric glenoid erosion may occur in glenohumeral OA (5). Patient-specific variations in magnitude and retroversion of glenoid bone loss in glenohumeral osteoarthritis pose a challenge for orthopaedic surgeons in joint reconstruction (6). Eccentric loading of the glenohumeral joint may lead to glenoid loosening which potentially requires revision surgery (7). Moreover, posterior glenoid erosion is a risk factor for poorer outcomes in function and pain (8) (9) (10). The management of glenoid erosion in shoulder arthroplasty demands individualized surgical techniques as well as implants to optimize outcomes and maximize implant longevity. Surgical techniques to address glenoid retroversion include eccentric reaming, glenoid bone grafts, augmented glenoid components, total shoulder arthroplasty, or specialized implants (7) (11). The “gold-standard” modality for assessment of complex glenoid anatomy to assist with surgical planning is 3D CT imaging (9) (12) (13). However, CT imaging exposes patients to radiation. Recently, 3D MR has been developed to characterize glenoid bone loss (14).

There is significant variation in glenoid morphology among patients with glenohumeral OA. Prior studies have discussed higher distributions of patients with glenoids who had posterior erosion and/or retroversion (15-18). To better guide treatment approaches, Walch et al. described glenoid morphology using CT scans in 113 shoulders between 1988 and 1995 (19). Specifically, the authors developed three broad classification types based on humeral head position, glenoid retroversion, and erosion pattern: Type A, Type B, and Type C. Types A and B have subgroups based on severity.

Three-dimensional reconstruction of CT images at the glenohumeral joint have reliably assisted surgeons with preoperative planning whereas two-dimensional (2-D) radiographs and CT scans may misrepresent important anatomical characteristics of the shoulder leading to insufficient evaluation of erosion (12) (13).

To mitigate radiation exposure from 3D CT, 3D MR could serve as an alternative for patients with end-stage glenohumeral OA indicated for shoulder reconstruction.

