### **Objective**

1. The primary objective is to evaluate the noninferiority of 3D MR when compared to 3D CT for characterizing bone morphology in patients with glenohumeral osteoarthritis.

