### **Hypothesis**

3D MR imaging provides the same information as 3D CT in characterizing glenoid morphology.

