### **Primary Endpoints**

- Differences and/or similarities in glenoid erosion and version measurements between of 3D CT and 3D MR.

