### **Outcome Measure Evaluation Criteria**

- Degree of concordance/discordance between interpretation from 3D CT and 3D MR

CONFIDENTIAL

This material is the property of the NYU School of Medicine and Langone Medical Center.  
Do not disclose or use except as authorized in writing by the study sponsor (if applicable).

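### The aim is noninferiority, but the plan names only difference tests and sets no margin, confidence-interval rule or success criterion

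*Combined protocol and SAP*

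**What the plan says.** - **Aim.** Study Summary, Purpose: "To examine the non-inferiority of three-dimensional (3D) magnetic resonance (MR) versus the gold-standard, 3D computed tomography (CT) imaging". The Purpose paragraph of section I repeats this, and Objective has "The primary objective is to evaluate the noninferiority of 3D MR when compared to 3D CT for characterizing bone morphology".
- **Hypothesis.** "3D MR imaging provides the same information as 3D CT in characterizing glenoid morphology".
- **Endpoint.** Primary Endpoints: "Differences and/or similarities in glenoid erosion and version measurements between of 3D CT and 3D MR". No size or direction is attached.
- **Evaluation criterion.** Outcome Measure Evaluation Criteria: "Degree of concordance/discordance between interpretation from 3D CT and 3D MR". No statistic or threshold is attached.
- **Analysis.** Data Analysis, and the Statistical Methodology row of the Study Summary: "Paired sample t-test to compare measurements by model and ANOVA to assess differences among modalities".
- **Sample size.** Sample Size Analysis gives a minimum of ten pairs from a paired t-test with alpha .05 and power .80. It states no difference, SD, margin or sidedness. Number of Subjects sets enrolment at 50.
- **Readings.** Under Visit 2, two observers measure 3D CT version on two occasions at least two weeks apart. MR version is measured by the same two observers with the same method. How these readings become one pair per patient is not stated.

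**The concern.** The stated question is whether MR is close enough to CT. A paired t-test or ANOVA, read in the usual way, takes no difference as its null hypothesis and asks whether the data contradict it. Failing to reject that null may only mean that the study is small or the readings noisy. Rejecting it may only mean that a trivial bias was measured precisely. Neither outcome says whether the difference is small enough, because the plan never says how small that is.

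At stake is the only objective the protocol states. Without a margin and decision rule fixed beforehand, any later statement that MR is noninferior would rest on a criterion chosen after the data were seen. If p>0.05 were taken as success, a smaller or noisier study would be more likely to succeed.

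**Working it through.** **Inputs from the protocol:** alpha .05, power .80, ten pairs (Sample Size Analysis); 50 patients (Number of Subjects). **Assumed, because the documents give none:** every SD, bias and margin below. SD means the SD of the paired MR-minus-CT differences.

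**1. The plan's own figure.** Power of a paired t-test comes from the noncentral t distribution with n − 1 degrees of freedom and noncentrality (bias/SD) × √n. Ten pairs cannot be derived forward, since no effect is stated. Solving backward for 80% power at n = 10 gives bias/SD = 0.996 (two-sided 5%) or 0.853 (one-sided 5%). Ten is therefore a possible answer for detecting a difference of roughly 1 SD. It is not the answer to a noninferiority question.

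**2. What a non-significant result means** (two-sided 5%; critical t = 2.262 at n = 10 and 2.010 at n = 50).

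| True bias | P(non-significant), 10 pairs | P(non-significant), 50 pairs |
|---|---|---|
| 0.3 SD | 0.86 | 0.45 |
| 0.5 SD | 0.71 | 0.07 |

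For 0.5 SD the noncentrality is 0.5 × √10 = 1.58 (power 0.293) and 0.5 × √50 = 3.54 (power 0.934).

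**3. What a significant result means.** Take 50 pairs, a true bias of 1 degree and an illustrative margin of ±2 degrees. Compare the t-test with two one-sided tests (TOST, one-sided 5%).

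| SD (degrees) | t-test significant | TOST shows equivalence |
|---|---|---|
| 2.00 | 93% | 97% |
| 2.92 | 66% | 77% |
| 4.69 | 32% | 43% |

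At SD 2 the planned test almost always reports a difference while the interval almost always lies inside the margin. The contrast is weaker at the larger SDs.

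**4. What 50 pairs can support.** Margin/SD needed for 80% power; the normal approximation is shown first and the exact t-based value second.
- One-sided noninferiority, 5%, no bias: (1.645 + 0.842)/√50 = 0.35; exact 0.36.
- TOST, one-sided 5%, no bias: (1.645 + 1.282)/√50 = 0.41; exact 0.42.
- TOST, one-sided 2.5%, no bias: (1.960 + 1.282)/√50 = 0.46; exact 0.47.
- TOST, one-sided 5%, true bias 0.1 SD: exact 0.46. At a margin of 0.42 SD, power falls to 70%.

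At ten pairs, TOST at one-sided 5% with no bias needs a margin of about 1.00 SD.

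**5. Why the reading rule matters.** Suppose the true MR-CT difference varies between patients with SD 2 degrees and each reading has an independent error of SD 3 degrees. Then SD = √(2² + 2 × 3²/k) for the mean of k readings per modality: 4.69 (k = 1), 3.61 (k = 2), 2.92 (k = 4). Multiplied by 0.42, the smallest margins with 80% TOST power are 2.0, 1.5 and 1.2 degrees. If one observer's repeat errors correlate at 0.5 to 0.8, the k = 4 SD is about 3.3 to 3.5 instead.

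**6. Why a margin on the mean is not enough.** With SD 4.69, margin 2 degrees (ratio 2/4.69 = 0.43) and no bias, TOST at 50 pairs passes 82% of the time. The 95% limits of agreement would be about ±1.96 × 4.69 = ±9.2 degrees. A rule on average bias alone could pass MR despite wide disagreement in individual patients.

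**The case against.** **A paired t-test can serve noninferiority.** It can be run against a shifted null, or its confidence interval compared with a margin. Data Analysis does not state the null hypothesis. This stands as far as it goes: a reader might infer that the data or the method are unfit for noninferiority, and they are not. But both routes need a margin, and there is none. The defect is the missing prespecification, and wording can repair it.

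**The concordance criterion supplies the decision rule.** It comes closest, but it has no statistic and no threshold, so no result could fail it.

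**Fifty patients far exceeds the ten-pair minimum.** Ten was computed for an unstated difference. A larger sample does not turn a difference test into a noninferiority test.

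**The reading problem is speculative.** Partly so. A reader might infer that the plan would enter each patient's four readings as independent pairs. Nothing says this; Sample Size Analysis speaks of pairs, and the planned number is 50 patients. What stands is that the reduction rule is unstated. The wording for MR may also carry over CT's two occasions, so unequal numbers of readings cannot be assumed.

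**The glenoid classification suggests a categorical outcome.** A reader might infer this from the Background, but the classification is described there only as earlier work and is not a planned outcome.

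**Conclusion.** The concern holds and should be fixed before the MR-CT comparison is run. The aim is noninferiority and the hypothesis is sameness. The only analyses named, and the test used for sizing, are difference tests on their ordinary reading, and the text available contains no margin, interval rule or success criterion. The sections where these belong are present and lack them. Followed as written, neither a significant nor a non-significant result would answer the objective.

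Two stronger conclusions do not follow. A reader might infer that 50 patients are too few. The documents cannot settle this: it depends on a margin and an SD they do not give, and the threshold moves from 0.36 to 0.47 SD with the choice of test, alpha and true bias. A reader might also infer that the ten-pair figure is an arithmetic error. It is attainable for a difference of about 1 SD; the fault is that the effect is unstated and the question is the wrong one.

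**What to change.** Before any MR-CT comparison is run:

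(a) The investigators prespecify and justify a margin for 3D version and one for the erosion measure.

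(b) Reduce the two observers' repeat readings to one value per patient per modality, for example the mean, by the same rule for CT and MR. Base the SD and power on that value.

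(c) Make the primary analysis a confidence interval for the mean paired MR-minus-CT difference, compared with the margin. TOST with a 90% interval is one option, suitable because version is a signed angle. State whether both measures must pass.

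(d) Because (c) covers average bias only, prespecify an agreement criterion to give the concordance measure a threshold, for example a maximum acceptable width for the Bland-Altman limits of agreement. Report the ICC as supportive. If the interpretation to be compared is categorical, define it and name a suitable statistic.

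(e) Keep the t-test and ANOVA as descriptive, and state that p>0.05 is not evidence of noninferiority.

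(f) Restate Sample Size Analysis as the power or precision that 50 pairs give for the chosen margins.

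**Cost.** Protocol and SAP wording, with no new scans or readers. Existing scans may need extra readings for erosion, or for MR if its readings were not repeated as for CT. The trial can then fail, or prove underpowered, on a stated criterion. Two-sided equivalence also costs some power: at one-sided 5% with no true bias, the margin needed at 50 pairs rises from 0.36 to 0.42 SD compared with one-sided noninferiority.

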### **DATA SAFETY MONITORING PLAN (DSMP)**

#### **I. Study Monitoring**

The co-investigator, [name] will be the data safety monitor for this project. After a three (3) months follow-up period, [name] will review the data for SAE's, protocol deviations and other issues. If it is determined that certain events occur above an expected rate (i.e. increased shoulder pain), then enrollment will be stopped.

#### **II. Types of Data**

Under this DSMP, the following data/events will be captured and documented:

- Radiologic images;
- Diagnostic radiology interpretations;
- Reportable and/or adverse events; and
- Protocol Deviations.

#### **III. Responsibilities and roles for gathering, evaluating and monitoring the data:**

Principal Investigator

#### **CONFIDENTIAL**

This material is the property of the NYU School of Medicine and Langone Medical Center.  
Do not disclose or use except as authorized in writing by the study sponsor (if applicable).

After six months following study initiation, the PI will meet with any co-investigators and the Research Coordinator to discuss the current findings and analysis. During these meetings, the PI will also be responsible for verifying data accuracy, and compliance with the study protocol.

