#### **Methods and Procedures**

##### Visit 1 -- Recruitment and Enrollment:

The study will employ convenience sampling of surgical candidates with glenohumeral osteoarthritis from the practice of the primary investigator, who is the treating surgeon. Immediately following his or her clinical visit with the primary investigator, each patient who is a candidate for shoulder arthroplasty will receive information on the study, including benefits and harms of participating in the study from the co-investigator at primary investigator's clinical office (NYU Langone Orthopedic Center). Written consent will be obtained from subjects based upon their medical condition (as determined by their physician). The consent process will take place during an office visit at which time the investigator has determined subject's voluntary participation has been upheld. Subjects will be informed about the study and the intended purpose. They will be given the opportunity to ask questions and receive thorough explanations. They will be made aware of the possible risks and anticipated benefits. They will also be informed of alternative procedures. Subjects will then be given another opportunity to ask questions and agree or disagree to consent. Potential subjects may enroll by providing informed consent with the co-investigator. The study will not exclude potential participants based on sex, race, and/or ethnicity. Subsequently, the study co-investigator will determine subject eligibility to participate in the study by obtaining information on potential contraindications of MR imaging, such as having prior history of injury involving metal or metallic particles as well as presence of medical implants, such as cardiac pacemakers.

This recruitment and enrollment visit should take no more than thirty (30) minutes.

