##### Visit 2 -- Preoperative Imaging:

Subjects will have both 3D CT and 3D non-contrast MR scheduled on the same day. The CT scan, which is standard of care, will be scheduled at NYU Langone Orthopedic Hospital followed by the MR, the investigational procedure, at NYU Langone Orthopedic Center. Before imaging, the subjects will be screened for potential contraindications to each imaging modality in accordance with institutional standard of care routine procedures. The standard of care CT imaging will take no more than 30 minutes while the investigational MR imaging will take no more than 60 minutes in duration. Each enrolled subject will receive a standard of care CT scan along with an investigational MRI scan of the shoulder girdle while supine. Each enrolled subject's CT imaging is not dependent on receiving prior MR imaging; he/she will not experience delays in receiving standard of care CT imaging as a result of study participation.

The CT protocol consists of 3-mm axial images of the glenoid reconstructed into 1-mm sagittal and coronal 2D reconstructions using the following parameters: 120 kV, 280 mA, and pitch of 0.9. The CT data were also used to produce a 3D reconstruction of each glenoid.

The 2D glenoid version is measured by 2 musculoskeletal-trained radiologists on 2 occasions, at a minimum of 2 weeks apart, with the observers blinded to each other's results. The 2 observers meet before obtaining data to review the appropriate technique for measuring glenoid version. The 2D glenoid version is determined using the method of Friedman et al (17) with the mid glenoid cut being determined by dividing the total number of axial cuts through the glenoid by 2 (20).

The 2D CT images are imported in Vitrea software. The 3D volume rendering model will be produced. The 3D glenoid version is measured by the same 2 observers on 2 occasions, at a minimum of 2 weeks apart, with the observers blinded to each other's results. Three points which were previously validated were first interactively placed on the Mimics 3D model by the observer: the inferior tip of the scapula body, the center of the glenoid surface, and the medial pole of the scapula, as described by Kwon et al. (12) As described in detail below, these points were used to define the transverse scapular plane, based

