#### Research Coordinator

The Research Coordinator will be responsible for providing data management support to the PI by collecting and documenting the required study data. This information will be documented in a secure Microsoft Excel spreadsheet with appropriate headings to distinguish the various types of data/events. The Research Coordinator will meet with the PI and any co-investigators to discuss the current findings/analysis, concerns/issues (unanticipated problems and adverse events), and the overall study in general.

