#### **V. Assessments**

After 6 months and 1 year following study initiation, the Principal Investigator, Co-Investigator(s) and Research Coordinator will review and assess the data and/or events captured under the DSMP.

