#### **VII. Procedures for Communicating – dissemination of safety information**

Outcomes of monitoring reviews will be communicated to the IRB through a yearly summary that will include a narrative on all adverse and reportable events (previously reported or not, serious or not), as well as any proposed changes to the protocol and/or study analysis.

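### The six-month monitoring meeting covers current findings and analysis, with no mask on the CT-MR comparison, no reading lock and no noninferiority margin fixed beforehand

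*Combined protocol and SAP*

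**What the plan says.** All of this is in the combined protocol and SAP.

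- **Data Safety Monitoring Plan (DSMP), Section III, Principal Investigator:** "After six months following study initiation, the PI will meet with any co-investigators and the Research Coordinator to discuss the current findings and analysis". The PI also verifies data accuracy and protocol compliance at these meetings.
- **DSMP Section III, Research Coordinator:** "The Research Coordinator will meet with the PI and any co-investigators to discuss the current findings/analysis, concerns/issues (unanticipated problems and adverse events".
- **DSMP Section II:** the captured data include radiologic images and "Diagnostic radiology interpretations", alongside adverse events and protocol deviations.
- **DSMP Section V:** "After 6 months and 1 year following study initiation, the Principal Investigator, Co-Investigator(s) and Research Coordinator will review and assess the data and/or events" that the DSMP covers.
- **DSMP Section VII:** the yearly summary to the IRB reports adverse events, "as well as any proposed changes to the protocol and/or study analysis".
- **Data Storage and Confidentiality:** the PI, co-investigators and research staff have database access for data analysis, with no limit on when.
- **Visit 2:** two musculoskeletal radiologists measure version twice, at least two weeks apart, "with the observers blinded to each" other's results. No other blinding of the readers is described.
- **Data Analysis:** one sentence naming a paired t-test and an ANOVA. It gives no margin and no interim rule, and Sample Size Analysis mentions no interim look either.

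**The concern.** A safety review does not need the CT-MR results. The meeting as worded takes in results as well as safety, and those attending run the study and have access to its data for analysis.

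Two things are exposed. The first is the analysis. The objective is noninferiority, but no margin is written down, and the primary endpoint is worded loosely enough to cover either differences or similarities. The criterion for success could therefore still be set after the running difference is known. The second is any reading not yet made. Observers place landmarks and select glenoid edges by hand, and the MR models also need manual segmentation. Someone who knows which way the two modalities differ can shift such measurements without meaning to.

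If either happened, a conclusion that MR gives the same information as CT would not be free of data-dependent decisions.

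**Working it through.** **1. Does the meeting cover safety only?** The coordinator's paragraph lists findings and analysis as one item, and unanticipated problems and adverse events as another. Section II counts radiology interpretations as DSMP data. Section I, by contrast, describes a three-month review for serious adverse events, deviations and other issues, with no mention of findings or analysis. Read together, the Section III wording goes beyond safety. One uncertainty remains: the interpretations in Section II could be clinical reports and not the research version measurements. The text does not say.

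**2. Is the comparison closed to anyone?** No section masks it, names a lock date for readings, or restricts who may see results before the end. Study Summary calls the study single-blinded and Study Design calls it double blinded. Neither says who is blind to what.

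**3. Is the analysis still open at six months?** Data Analysis names two tests and no margin, and no other section supplies one.

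**4. Could readings be influenced?** Visit 2 describes three points placed interactively, anterior and posterior glenoid edges chosen by hand, and, for MR, regions of interest and manual segmentation. The readers are blinded only to each other. The documents do not say whether either radiologist is a co-investigator, so this route is conditional on a reader attending or being told.

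**5. How many subjects come after the meeting?** The plan gives no figure to reproduce. The inputs are 50 subjects (Number of Subjects), a meeting at 6 months (DSMP Section III) and a total duration of 12 months (Study Summary). The length of accrual, A months, is not given. Assuming uniform accrual:

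subjects still to be enrolled = 50 × (1 − 6/A)

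| A (assumed) | Enrolled by month 6 | Still to be enrolled |
|---|---|---|
| 12 months | 50 × 6/12 = 25 | 25 |
| 9 months | 50 × 6/9 = 33.3 | about 17 |
| 6 months | 50 × 6/6 = 50 | 0 |

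Because second readings follow at least two weeks after the first, some readings can be outstanding when no subject remains to be enrolled. The documents do not allow that number to be fixed.

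**The case against.** The strongest reply is that the wording is loose, not harmful. The design is single-arm and within-subject, so no treatment allocation can be unblinded. No test or decision on results is stated for the meeting, and the readers are not listed as attending. This answer has force, and it rules out several stronger inferences.

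- **That half the sample is affected.** The 25 of 50 holds only for uniform accrual over the whole 12 months. That figure is a study duration, not an accrual period, and repeat readings and analysis may have to fit inside it.
- **That the readers are unblinded.** No section makes a reader a co-investigator or an attendee, and the rule that observers are blind to each other still stands.
- **That recruitment is steered.** It is true that "The study will employ convenience sampling of surgical candidates with glenohumeral osteoarthritis from the practice of the primary investigator", who would see the findings. But each subject enrols before either study scan and then has both, so the surgeon would have to predict the CT-MR difference in advance. This pathway is weak.
- **That enrolment may stop between ten and 50 on the results.** Ten pairs is the minimum from the power calculation and 50 is the planned number. The stopping provisions in DSMP Sections I and VI depend on events and risk, not on CT-MR results.
- **That the yearly summary licenses analysis changes.** Section VII is a duty to report proposed changes. Deleting it would remove a disclosure and prevent nothing.
- **That type I error is inflated.** Unadjusted two-sided 0.05 tests at 25 and at 50 subjects would give about 0.083 overall (correlation √(25/50) = 0.707). But no such test is planned, and extra rejections of no difference would count against the study's hypothesis.

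What the reply does not answer is that findings and analysis are to be discussed during the study, with nothing masked and no margin fixed.

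**Conclusion.** The concern holds in limited form. The plan schedules a discussion of current findings and analysis halfway through the stated duration, does not mask the CT-MR comparison, and leaves the noninferiority criterion unset. The exposure of the analysis follows from the text if findings include the research measurements, which is the natural reading. The exposure of the readings depends further on a reader attending or being told.

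The size cannot be fixed. From 0 to about 25 of 50 subjects remain to be enrolled, under uniform accrual over 6 to 12 months, and outstanding readings may go beyond that. No bias in the result has been shown or quantified. The change is worth making because it costs almost nothing and safety monitoring does not need the comparison.

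**What to change.** - **DSMP Section III (both paragraphs) and Section V:** state that meetings before the last reading is locked cover only accrual, adverse events, protocol deviations, and scan and data completeness and accuracy, with no CT-MR comparison shown. The PI keeps the duty to verify accuracy; the checks are done without comparing the two modalities.
- **Data Storage and Confidentiality:** apply the same time limit to access to the research readings. Otherwise the database leaves open what the meeting rule closes.
- **Visit 2:** state that the two readers see no CT-MR comparison and no other observer's readings until lock.
- **Exception:** state that the standard-of-care CT and its clinical report stay available to the treating surgeon throughout.
- **DSMP Section VII:** keep the reporting duty, and add that any change to the study analysis must be dated and made before comparative results are seen. The noninferiority margin should be fixed under the same rule.

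The cost is protocol wording and a wait: investigators see no comparative results until the readings are locked. Safety monitoring loses nothing.
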